1. BACKGROUND	
2. RATIONALE	
3. THEORETICAL FRAMEWORK	
4. RESEARCH QUESTION/AIM(S)	
5. STUDY DESIGN/METHODS	
6. STUDY SETTING	
7. SAMPLE AND RECRUITMENT	
8. ETHICAL AND REGULATORY COMPLIANCE	
9. DISSEMINATION POLICY	
10. REFERENCES	
11. APPENDICES	

KEY STUDY CONTACTS				
Chief Investigator	[name]			
	Academy Office			
	Great Western Hospital			
	[name]			
	Swindon			
	[name]			
	[contact]			
	[name]			
Study Co-ordinator	[name]			
Sponsor	University of Bristol			
	[contact]			
	Sponsor representative:			
	[name]			
	Sponsor contact:			
	[name]			
	Head of Research Governance			
	Research Governance Team			
	Research & Enterprise Division			
	University of Bristol			
	[name],			
	[name],			
	[name]			
	T: [name]			
	M: [name]			
	[contact]			
	General Enquiries: [contact]			
Joint-sponsor(s)/co-sponsor(s)	N/A			
Funder(s)	This study is funded internally by Great Western Hospital Academy			
Key Protocol Contributors	[name]			

STUDY SUMMARY			
Study Title	Anaesthetic pre-operative Assessment of the adult Airway and Non-Specialist video Assessment: a method-compariso study		
Internal ref. no. (or short title)	AAANSA		
Study Design	Method-Comparison Study		
Study Participants	Attending a pre-operative remote video assessment clinic prior to an operation under general anaesthesia		
Planned Size of Sample (if applicable)	200 patients		
Follow up duration (if applicable)	N/A		
Planned Study Period	Estimated duration for the main protocol (e.g. from start of screening to last subject processed and finishing the study) is approximately 1 year		
Research Question/Aim(s)	Primary aim:		
	To determine whether non-specialist remote video assessment of the airway is comparable to in-person anaesthetic assessment of the airway		
	Secondary aims:		
	To determine how the quality of remote video airway assessment can be optimised		
	To determine which elements of the airway assessment can be adequately assessed remotely		

FUNDING AND SUPPORT IN KIND			
FUNDER(S)	FINANCIAL AND NON-FINANCIAL SUPPORT GIVEN		
[name]	Providing financial support for the study		
Great Western Hospital Academy			
[name]			
Swindon			
[name]			

ROLE OF STUDY SPONSOR AND FUNDER

Study sponsor: University of Bristol

Role of study sponsor: assuming overall responsibility for the initiation and management of the study. The University of Bristol will provide support in the form of advice on study design, conduct, data analysis and interpretation. They will review the IRAS application for Heath Research Authority ethical approval.

PROTOCOL CONTRIBUTORS

The protocol was conceived and designed by [name] (lead investigator).

The University of Bristol Research Governance Team provided advice on:

[figure not shown]
- Study design
- Conduct
- Supporting the application for IRAS ethical approval

Great Western Hospital Academy, the study funder, will not control study design, analysis, interpretation or manuscript writing.

KEY WORDS:

Anaesthetic airway remote video assessment telemedicine

STUDY FLOW CHART

Abbreviations			
CRF	Case Report Forms		
GWH	Great Western Hospital		
HRA	Health Research Authority		
IRAS	Integrated Research Application System		
NHS	National Health Service		
PIS	Patient Information Sheet		
REC	Research Ethics Committee		

STUDY PROTOCOL

Anaesthetic pre-operative Assessment of the adult Airway and Non-Specialist video Assessment: a method-comparison study

1 BACKGROUND

For patients undergoing general anaesthesia, anaesthetists attempt to predict difficult tracheal intubation using a variety of anatomic predictors and bedside tests^[1]. When difficulty is suspected, these predictions should be used to inform the clinician's approach to airway management, including a 'rescue' approach, should difficulty be encountered^[2]. Airway assessment also helps to determine if additional precautions are needed prior to starting intubation of the airway^[2].

Meta-analysis has given clinicians insight into which assessments help to predict difficult tracheal intubation, and how successful they are at doing so^[1]. However, the evidence base for remote video assessment of the airway is lacking^[3]. A single study, published in 2013, suggested similar sensitivity in predicting difficult tracheal intubation between remote and in-person airway assessment^[4]. However, this study used tele-medicine technology, which consisted of non-portable, high-definition, video-streaming equipment with dedicated lighting. This represents a very different method of assessment to what is being utilised by many NHS hospitals during the SARS-CoV-2 outbreak.

Since the onset of the pandemic, face-to-face assessments have been largely replaced by virtual clinics^[5]. As Cook (2021) points out, this has the potential to reduce the opportunities to perform airway assessment, and to impact on the accuracy of the assessment itself. In our hospital's preoperative department, patients are now invited to a remote video consultation with a nurse practitioner or healthcare assistant. Patients that are due to undergo an operation under general anaesthesia, are invited to a video consultation using a text messaging service. This results in the patient joining the consultation using the front-facing camera of their mobile phone device. We believe our experiences of pre-operative assessment reflect the wider picture across the United Kingdom^[6]. This rapid and unprecedented change away from traditional in-person assessment is yet to be properly studied, and many questions remain unanswered.

We will assess remote video airway assessment by non-specialist healthcare providers and compare the results to a face-to-face assessment. We also aim to determine the common limitations to remote assessment, in order to issue recommendations for optimising the consultation.

2 RATIONALE

2.1 Primary question:

• Is pre-operative non-specialist remote video assessment of the adult airway comparable to inperson assessment of the airway?

The primary aim is to determine if the findings from the remote video non-specialist airway assessment correlate with the results of an in-person anaesthetic assessment. A literature review of telemedicine anaesthetic assessment by Bridges et al. in 2020 revealed a single randomised controlled trial that compared remote airway evaluation to in-person assessment. The findings suggested comparable sensitivities, but the study was performed using non-portable, high-definition, video-streaming equipment with dedicated lighting. This limits the generalisability of the findings to our patient population, who are using mobile phone devices to connect to the videocall.

2.2 Secondary question(s):

How can the quality of remote video airway assessment be optimised?

This question looks to determine how often video assessment is unacceptable, what factors make the assessment unacceptable, and what recommendations can be drawn from these findings to optimise the assessment.

Which elements of pre-operative airway assessment can be adequately assessed remotely?

This question will help determine whether some of the traditional anatomic markers and tests can be easily assessed using remote video consultation. There are practical considerations when undertaking mobile device videocalls that may impact the adequacy of the assessment. For example, assessment of the mouth may be frequently impaired by inadequate lighting.

3 THEORETICAL FRAMEWORK

Airway assessment and the management of the difficult airway has consistently been a topic of interest in anaesthesia research and in clinical practice guidelines. The SARS-CoV-2 pandemic has caused a significant shift away from face-to-face consultations and towards virtual assessment. This has the potential to impact upon the accuracy of difficult airway prediction and which could ultimately lead to detrimental patient outcomes.

"Optimising the quality of remote airway assessment and exploring whether it correlates with face-to-face assessment" was an area identified as worthy of research in the Association of Anaesthetists COVID-19 airway management guidance^[5].

We theorise that virtual airway assessment can be used as a valid tool to provide comparable results to in-person anaesthetic assessment. We will collect and collate data to establish the reality using quantitative methods, comparing the results using kappa analysis^[11].

Furthermore, we will enquire on the limitations of virtual assessment by using a qualitative, interpretative approach whereby we find meaning from the personal experience and perspectives of the assessors^[12].

Hypotheses:

- Video assessment of the airway will provide comparable results to in-person assessment of the airway for the following measurements:
 - Mallampati score
 - Upper lip bite test
 - Lower jaw protrusion

- Video assessment of the airway will provide discordant results to in-person assessment of the airway for the following measurements:
 - Mouth opening
 - o Thyromental distance
- Technical limitations experienced during the video assessments are likely to have a greater impact on the adequacy of certain airway measurements than others

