4.2 Outcome

The study outcomes are:

- To determine whether remote video assessment of the adult airway is a suitable alternative to in-person anaesthetic assessment
- Formulate recommendations that may help with optimising future remote video airway assessments

5 STUDY DESIGN and METHODS of DATA COLLECTION AND DATA ANALYIS

This is a single centre, method-comparison study that does not involve an intervention, but does involve the gathering and comparison of patient data. Patients that meet the eligibility criteria will be contacted by researchers using their telephone number. The participants will be provided with a participant information sheet via email, and given time to read the information. This will include information on the nature, significance, implications and risks of the trial and the participant will have the right to withdraw from the trial at any time. The researcher will then give the participant the opportunity to ask questions regarding the study. If the participant agrees to take part in the study, they will be sent an electronic consent form for them to record their consent. Consenting patients will be given a unique study identifying number which will be recorded on a password-protected database held on Great Western Hospital's servers.

Data collection

The study design will be a method-comparison study. This will involve the collection of the patient's airway data via two separate methods, and compare the results. Healthcare professionals working

within the pre-operative assessment clinic at Great Western Hospital are already completing remote video assessments of the airway. As part of the study, they will collect additional data on airway assessment tests and anatomical markers. The data collection points used for airway assessment will be based on the current literature evidence base. The meta-analysis published by Roth et al.^[1] identified the following bedside airway assessment tests with an underlying evidence base:

- Modified Mallampati^[7]
- Thyromental distance^[8]
- Mouth opening^[9]
- Upper lip bite test^[10]

The following tests were identified from the British Journal of Anaesthesia review on predicting difficult intubation^[13]:

- Neck movement
- Lower jaw protrusion

The healthcare professional conducting the assessment will also be asked to record any technical problems or limitations that impeded their assessment of the airway.

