The results will be recorded using paper forms designed by the researcher, which will be stored within a locked cabinet on NHS premises until it is entered onto a password-protected database on the hospital's servers. This will happen as soon as possible and the database will only be accessible to the research team. The unique study identifier will be linked to the individuals' personal data on a separate password-protected database held on the hospital's servers.

No video footage or still images will be stored or recorded.

The data will be archived according to the Sponsor's standard operating procedure.

Patients' demographics will be described using frequency and proportion for categorical data and means and standard deviations for continuous data. A comparison between the results of the two airway assessments made by the non-specialist and the anaesthesiologist will be conducted on each of the airway measurements using kappa analysis.

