6 STUDY SETTING

The study will take place at Great Western Hospital, Swindon, and is a single centre study.

Participants will be identified via the Great Western Hospital Pre-Operative Assessment Clinic. Potential participants will be contacted by the researcher via telephone prior to their attendance at the pre-operative clinic in-order to provide the participant information (via email), check eligibility criteria and gain electronic consent using the Microsoft Forms online platform. Microsoft forms is compliant with GDPR and the Data Protection Act (2018). The consent forms will be password protected, with access granted on an individual basis to select members of the research team.

Prior to recruitment start, staff will undergo the relevant training and receive the necessary information, either remotely, or face-to-face. Pre-operative assessment staff already perform remote video airway assessments as part of their day-to-day job. Data will be collected in the pre-operative assessment clinic and in the operating theatre for the remote video assessment and the in-person assessment respectively. Both data sets will initially be recorded onto paper forms and then transcribed to a secure database, as outlined in section 5. Any paper forms will immediately be disposed of in-keeping with the hospital confidential waste policy.

Participants will be considered eligible for enrolment into this study if they fulfil all of the inclusion criteria and none of the exclusion criteria as defined in section 7.

Using Great Western Hospital is an appropriate setting for this study as it already has an operational video-calling system in place that adheres to the principles of GDPR and meets the necessary data security standards. The hospital also has a research and innovation department that is willing to review the study protocol and support the study through local feasibility approval processes.

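### Section 4.2 draws a suitability conclusion from kappa alone, which does not fix how often video misses an in-person positive, and no airway-management outcome is listed for collection

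*Protocol*

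**What the plan says.** Section 1 gives prediction of difficult intubation as the purpose of airway assessment. It cites the one earlier remote comparison because it "suggested similar sensitivity in predicting difficult tracheal intubation between remote and in-person airway assessment". Section 3 then names the risk of moving to virtual assessment: "This has the potential to impact upon the accuracy of difficult airway prediction and which could ultimately lead to detrimental patient outcomes".

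The aim is narrower. Section 2.1 asks "if the findings from the remote video non-specialist airway assessment correlate with the results of an in-person anaesthetic assessment". Section 5 describes collecting the patient's "airway data via two separate methods, and compare the results", and lists six bedside tests. The video assessor is also asked to "record any technical problems or limitations that impeded their assessment of the airway", and section 8.6 adds basic demographics. On timing and place, section 6 states: "Data will be collected in the pre-operative assessment clinic and in the operating theatre for the remote video assessment and the in-person assessment respectively". The comparison "will be conducted on each of the airway measurements using kappa analysis" (section 5).

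The first study outcome in section 4.2 is nevertheless: "To determine whether remote video assessment of the adult airway is a suitable alternative to in-person anaesthetic assessment".

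**The concern.** There are three layers, and they do not quite line up. The rationale is predictive accuracy, the data and analysis are agreement, and the conclusion is suitability. Two things are at stake.

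- **What the conclusion can bear.** Someone reading that video is suitable, after an introduction about missed difficult airways, will take it as reassurance about missed cases. Kappa is one symmetric number. It shows neither the direction of disagreement nor the share of in-person positives that video fails to flag.
- **A missed opportunity that closes.** Participants are enrolled ahead of a general anaesthetic (section 7.1.1), and a study form is already completed in theatre. No item on what happened to the airway is listed. Section 8.6 deletes personal data once the final dataset is transferred, so such items would be hard to recover afterwards.

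**Working it through.** **Inputs.** From section 7.2.1: positive proportion p = 0.7 (q = 0.3), null kappa 0.5, kappa to detect 0.7 (also the threshold for good agreement), unbiased assessors, 173 subjects calculated, 200 planned. Assumed, because no figures are given: two-sided alpha 0.05 and 80% power. Also assumed: incidence of difficult intubation 2% to 10%.

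**1. The plan's own figure.** For two raters with common marginals the cells are p² + κpq, 2pq(1 − κ) and q² + κpq.

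- κ = 0.5: 0.595, 0.210, 0.195
- κ = 0.7: 0.637, 0.126, 0.237
- Sum of (difference)²/null cell: 0.042²/0.595 + 0.084²/0.210 + 0.042²/0.195 = 0.00296 + 0.03360 + 0.00905 = 0.0456
- n = (1.960 + 0.842)²/0.0456 = 172.1, rounded up to 173

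The stated 173 is reproduced. No prediction or outcome measure enters it, so nothing below changes it.

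**2. Discordant pairs per test.** The share is 2pq(1 − κ).

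- κ = 0.7: 2 × 0.7 × 0.3 × 0.3 = 0.126, about 25 of 200
- κ = 0.5: 2 × 0.7 × 0.3 × 0.5 = 0.21, or 42 of 200

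**3. Miss rate at a fixed kappa.** With equal marginals, the share of in-person positives that video calls negative is pq(1 − κ)/p = (1 − p)(1 − κ). At κ = 0.7:

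| Proportion positive | Video misses | In 200 patients |
|---|---|---|
| 0.7 | 0.3 × 0.3 = 9% | 12.6 of 140 |
| 0.3 | 0.7 × 0.3 = 21% | 12.6 of 60 |
| 0.1 | 0.9 × 0.3 = 27% | 5.4 of 20 |

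The protocol does not say which finding counts as positive. If the 0.7 refers to favourable findings, adverse findings make up 0.3 and the 21% row applies to them.

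**4. Symmetry.** As an illustration, drop the unbiased-assessor assumption and let all 12.6% of discordant pairs be video misses, with 70% positive in person. Video is then positive in 57.4%.

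- Observed agreement: 0.574 + 0.300 = 0.874
- Chance agreement: 0.7 × 0.574 + 0.3 × 0.426 = 0.530
- Kappa: (0.874 − 0.530)/(1 − 0.530) = 0.73

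Video misses 0.126/0.7 = 18% of in-person positives here. Transpose the table, so that video misses none and over-calls instead, and kappa is still 0.73.

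**5. What an added outcome could show.**

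- All patients: 200 × 0.02 = 4 to 200 × 0.10 = 20 difficult cases. This is an upper figure, because eligibility requires general anaesthesia, not intubation.
- Among discordant pairs, per test: 25.2 × 0.02 = 0.5 to 25.2 × 0.10 = 2.5, both directions together, if difficulty is no commoner there than elsewhere.
- Precision: a sensitivity near 0.8 would have an exact 95% interval of 0.19 to 0.99 (3 of 4) up to 0.56 to 0.94 (16 of 20).

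**The case against.** The strongest reply is that this is openly a method-comparison study. The primary question, the first objective, the analysis and the sample size all concern agreement. The guidance quoted in section 3 itself asks whether remote assessment correlates with face-to-face assessment. The sentence about harm is background, not an endpoint. Section 4.2 speaks of an alternative to in-person assessment, which is a relative claim. All of that stands, and the agreement aim needs no defence.

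Three stronger readings are tempting and should not be taken from the documents.

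- **That the trial fails because it cannot say which reading was right in a discordant pair.** Intubation difficulty would not verify an individual Mallampati or mouth-opening reading. At most it shows which reading better predicted difficulty, and only 0.5 to 2.5 such cases per test are expected among discordant pairs.
- **That it is a defect to score a pair as agreement when both methods miss a difficult airway.** For a substitution question that scoring is proper: video did no worse than the practice it would replace.
- **That airway outcome would be an independent arbiter.** Section 1 says predictions inform the approach to airway management, so the in-person reading can alter the technique and thus the outcome.

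The case report form and flow chart are not shown. The absence of outcome items is inferred from the data items that the protocol describes.

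What the reply does not answer is that even a relative claim of suitability depends on how often, and in which direction, video departs from the in-person reading. Kappa does not report that.

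**Conclusion.** The point holds as a mismatch between conclusion and data, together with a cheap improvement. It does not invalidate the design. A kappa meeting the protocol's own standard of good agreement is compatible with video missing 9% to 27% of in-person positives, for positive proportions from 70% down to 10% and equal marginals. About 25 of 200 patients per test would still be discordant at the planning values. Good agreement on kappa is therefore not enough to support suitability, and it says nothing directly about predictive accuracy or safety.

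The miss rates rest on dichotomised tests and equal marginals, as in the sample-size paragraph. The event counts rest on an assumed incidence that the documents do not give.

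**What to change.** 1. **Whether or not any field is added**, state the 4.2 conclusion as agreement with in-person assessment, and say that it is not evidence of predictive accuracy or safety. This costs one sentence.
2. **Report discordant pairs by direction for each test**: video negative with in-person positive, and the reverse. This needs no new data.
3. **Before recruitment, add to the in-person form**: the airway technique used, the laryngoscopic view and number of attempts if intubated, and whether unanticipated difficulty occurred. Tabulate these descriptively by the four video/in-person combinations, labelled exploratory.

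The third item costs a few form fields and a line in the information sheet, with no extra patient, assessor or procedure. That these items are routinely charted is an assumption to confirm locally. The drawbacks are few events and an outcome that the in-person reading may influence.

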4 RESEARCH QUESTION/AIM(S)

Aim:

The aim of the study is to evaluate the use of non-specialist remote video assessment of the adult airway in the pre-operative environment

4.1 Objectives

The study's objectives are:

- Compare the results of non-specialist remote video assessment of the adult airway to inperson anaesthetic assessment
- Identify common problems that impair the quality of remote video airway assessment
- Identify the frequency with which airway assessment tests fail to be adequately assessed remotely

4.2 Outcome

The study outcomes are:

- To determine whether remote video assessment of the adult airway is a suitable alternative to in-person anaesthetic assessment
- Formulate recommendations that may help with optimising future remote video airway assessments

5 STUDY DESIGN and METHODS of DATA COLLECTION AND DATA ANALYIS

This is a single centre, method-comparison study that does not involve an intervention, but does involve the gathering and comparison of patient data. Patients that meet the eligibility criteria will be contacted by researchers using their telephone number. The participants will be provided with a participant information sheet via email, and given time to read the information. This will include information on the nature, significance, implications and risks of the trial and the participant will have the right to withdraw from the trial at any time. The researcher will then give the participant the opportunity to ask questions regarding the study. If the participant agrees to take part in the study, they will be sent an electronic consent form for them to record their consent. Consenting patients will be given a unique study identifying number which will be recorded on a password-protected database held on Great Western Hospital's servers.

Data collection

The study design will be a method-comparison study. This will involve the collection of the patient's airway data via two separate methods, and compare the results. Healthcare professionals working

within the pre-operative assessment clinic at Great Western Hospital are already completing remote video assessments of the airway. As part of the study, they will collect additional data on airway assessment tests and anatomical markers. The data collection points used for airway assessment will be based on the current literature evidence base. The meta-analysis published by Roth et al.^[1] identified the following bedside airway assessment tests with an underlying evidence base:

- Modified Mallampati^[7]
- Thyromental distance^[8]
- Mouth opening^[9]
- Upper lip bite test^[10]

The following tests were identified from the British Journal of Anaesthesia review on predicting difficult intubation^[13]:

- Neck movement
- Lower jaw protrusion

The healthcare professional conducting the assessment will also be asked to record any technical problems or limitations that impeded their assessment of the airway.

The results will be recorded using paper forms designed by the researcher, which will be stored within a locked cabinet on NHS premises until it is entered onto a password-protected database on the hospital's servers. This will happen as soon as possible and the database will only be accessible to the research team. The unique study identifier will be linked to the individuals' personal data on a separate password-protected database held on the hospital's servers.

No video footage or still images will be stored or recorded.

The data will be archived according to the Sponsor's standard operating procedure.

Patients' demographics will be described using frequency and proportion for categorical data and means and standard deviations for continuous data. A comparison between the results of the two airway assessments made by the non-specialist and the anaesthesiologist will be conducted on each of the airway measurements using kappa analysis.

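### Call conditions are recorded only if they impeded the video assessment, so failure rates with and without a condition cannot be estimated and the optimisation advice rests on assessor attribution

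*Protocol*

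**What the plan says.** The Study Summary gives a secondary aim: "To determine how the quality of remote video airway assessment can be optimised". Section 2.2 spells it out as finding "how often video assessment is unacceptable, what factors make the assessment unacceptable, and what recommendations can be drawn from these findings". Section 4.1 turns this into two objectives: "Identify common problems that impair the quality of remote video airway assessment" and "Identify the frequency with which airway assessment tests fail to be adequately assessed remotely". Section 4.2 makes recommendations for future video assessments a study outcome.

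The data for this come from one sentence in section 5 (Data collection): the healthcare professional is "asked to record any technical problems or limitations that impeded their assessment of the airway". Section 3 adds that "we will enquire on the limitations of virtual assessment by using a qualitative, interpretative approach", but no interview, focus group or other input from assessors is described. Section 3 also hypothesises that technical limitations affect some airway measurements more than others.

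Sections 5 and 8.6 say that no footage is kept, and section 6 says that paper forms are disposed of after transcription. Section 8.6 describes the clinic form as holding data similar to what the service already collects, plus basic demographics. No section provides for noting lighting, connection or camera conditions on every call.

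**The concern.** Recording depends on the assessor's own judgement that a problem got in the way. Poor light in a call that went well is not written down, so the number of poorly lit calls is unknown. To say that a factor makes assessment fail, one needs the failure rate when it is present and the rate when it is absent. The field described supplies neither denominator.

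At stake is the basis for the advice that the study means to issue. The data would show what assessors held responsible, with no means of checking those attributions against how often the same condition was harmless. The gap arises at data collection, so no later analysis plan can close it.

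**Working it through.** **The plan's own figure.** The protocol gives no rate for technical problems. Its only calculation, in section 7.2.1, is for the primary aim: null kappa 0.5, kappa to detect 0.7, proportion positive 0.7. It gives no numerical alpha or power; I assume 0.05 two-sided and 0.80. The goodness-of-fit formula is n = (z for alpha/2 + z for power)² / Σ[(π1 − π0)²/π0].

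- Cells under 0.5: 0.595, 0.210, 0.195. Cells under 0.7: 0.637, 0.126, 0.237.
- Sum: 0.042²/0.595 + 0.084²/0.210 + 0.042²/0.195 = 0.0456.
- n = (1.960 + 0.842)²/0.0456 = 172.1, rounded up to 173, as stated.

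That figure does not bear on this point. I take only the planned 200 participants from it, as the number of calls.

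**What can be estimated.** With all 200 calls as denominator and assumed frequencies of a reported problem, the 95% Wilson intervals are:

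| Assumed frequency | Interval |
|---|---|
| 10% | 6.6% to 14.9% |
| 20% | 15.0% to 26.1% |
| 30% | 24.1% to 36.7% |

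A problem present in 2% of calls would occur at least once with probability 1 − 0.98^200 = 0.98. Counting problems is therefore feasible.

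**What cannot be estimated.** Let e be the share of poorly lit calls, f1 the failure rate in them and f0 the rate in the others. Assume that every failure in a poorly lit call is recorded as a lighting problem. The records number 200 × e × f1, which does not involve f0. With f1 = 30%:

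| e | Lighting records | All failures if f0 = 10% (risk ratio 3) | All failures if f0 = 30% (risk ratio 1) |
|---|---|---|---|
| 20% | 12 | 12 + 16 = 28 | 12 + 48 = 60 |
| 40% | 24 | 24 + 12 = 36 | 24 + 36 = 60 |
| 60% | 36 | 36 + 8 = 44 | 36 + 24 = 60 |

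The total number of failures differs between the last two columns, so one might hope to use it as well. It does not settle the matter, because e is still unknown. Hold both observable counts at 24 lighting records and 36 failures, and let e vary:

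| e | f1 | f0 | Risk ratio |
|---|---|---|---|
| 20% | 24/40 = 60% | 12/160 = 7.5% | 8 |
| 40% | 24/80 = 30% | 12/120 = 10% | 3 |
| 60% | 24/120 = 20% | 12/80 = 15% | 1.3 |
| 66.7% | 24/133.3 = 18% | 12/66.7 = 18% | 1 |

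Two counts cannot determine three unknowns. The same data fit anything from a strong effect to none.

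**With conditions noted on every call.** At e = 40% the contrast is 24/80 against 12/120, a difference of 20 percentage points. Its standard error is √(0.3 × 0.7/80 + 0.1 × 0.9/120) = 0.058, so the 95% Wald interval is about 9 to 31 points.

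**The case against.** The strongest reply is that the protocol promises no contrast of failure rates. Its objectives are to identify common problems and count inadequate tests, its stated approach to limitations is qualitative, and its recommendations are offered only as possibly helpful. This largely stands. A reader might infer that the optimisation aim cannot be answered at all; the documents do not support that. What remains is that section 2.2 also asks what makes assessment unacceptable, and counts of blamed problems answer that only as far as the blame is right.

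Second, a reader might infer that there is no comparison with calls that went well. That also goes too far. Calls with no reported problem stay in the dataset with their airway results, giving a denominator and a crude comparison of agreement with and without a reported problem. Nor does impeding mean failing: an impeded assessment may still be completed. But the lighting or connection in the unreported calls is unknown, so they cannot act as comparators for a particular condition.

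Third, assessors may attribute correctly; poor light hiding the mouth is directly visible. With perfect attribution and e = 40%, they would record only the excess failures: 80 × (0.30 − 0.10) = 16 under risk ratio 3, and none under risk ratio 1. The field would then separate the two cases. This is fair, and it is why the conclusion is about reliance on attribution. For the same reason it does not follow that a common harmless condition would head the list. Suppose 40 of 200 calls are poor. A harmless condition in 30% of calls appears in 0.30 × 40 = 12 of them; a harmful one in 5% of calls that ruins 80% appears in 200 × 0.05 × 0.80 = 8. For the harmless one to rank first, assessors would have to blame it wrongly in at least 9 of 12, which nothing in the protocol suggests.

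Finally, the case report form is not shown and may already hold such items. That cannot be excluded. The protocol's own specification, however, is conditional on impediment.

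**Conclusion.** The point holds in a limited form. As section 5 is written, the study can report how often assessors met impeding problems and how often tests were inadequate, but not the failure rate with and without a given condition. In the illustration, 24 lighting records and 36 failures fit risk ratios from 8 down to 1, depending on how common poor lighting was, which is not recorded. The factors named under section 2.2 and the recommendations under section 4.2 would rest on assessor attribution alone.

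This assumes that the form follows section 5. All the rates are mine, since the protocol gives none, and the fixed count of 24 assumes that every failure in a poorly lit call is put down to lighting. Only a secondary aim is affected. The kappa comparison and the sample size of 173, raised to 200, are untouched.

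**What to change.** In section 5, require a short present/absent checklist on every video call, whether or not anything went wrong: lighting, connection, camera steadiness and angle, and helper present. It should be updated if conditions change during the call. Beside it, put an adequate/inadequate tick for each airway test, which would also serve the section 3 hypothesis about differing impact across tests. Keep the existing question about impeding problems as free text.

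Report inadequacy with and without each condition as a descriptive contrast with confidence intervals, and draw on it for the section 4.2 recommendations. Rare conditions will be imprecise: 8 failures in 10 calls has a 95% Wilson interval of about 49% to 94%, unadjusted for other conditions.

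The cost is under a minute per call and a simple cross-table, with no extra patients or staff. The items remain assessor judgements, so the contrast reduces the reliance on attribution without removing it. If the form already holds these items, one sentence in section 5 is enough.
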